11.2 Adverse events

11.2.1 Definition of treatment-emergent AE

AEs will be classified as either pre-study or treatment-emergent. Pre-study AEs are defined as AEs which had onset prior to the date of the first dose of BRV. TEAEs are defined as AEs that had onset on or after the day of first BRV dose. AEs with an incomplete onset date will be classified as TEAEs if the month and year of onset (when only the month and year are specified) is the same as the month and year of the first BRV dose or the year of onset (when only year is specified) is the same as the year of first BRV dose.

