#### **11.1.15 Adverse Events (AEs)**

At the Entry Visit, the Investigator will record any adverse event that was still ongoing at the end of the previous study. From the entry Visit onwards, adverse events will be assessed at each visit and recorded in the CRF and in the source documents. The study participant will be given the opportunity to report AEs spontaneously. A general prompt will also be given to detect AEs, e.g., "Did you notice anything unusual about your health (since your last visit)?" In addition, the Investigator should review any self-assessment procedures (e.g. daily record cards) used in the study.

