#### ***13.1.2 Efficacy and Safety Variables***

Primary safety variables:

- Occurrence of a TEAE
- Withdrawal due to an AE
- Occurrence of an SAE

Other safety variables:

- Laboratory tests (hematology, blood chemistry, urinalysis)
- Vital signs (systolic blood pressure [SBP]), diastolic blood pressure [DBP], pulse rate and body weight
- Electrocardiogram (ECG)
- Physical and neurological examinations
- Change in Hospital Anxiety and Depression Scale (HADS) scores from the Baseline of the previous study to each assessment for the first 2 years and to the last Evaluation Period assessment during the first 2 years

Secondary efficacy variables:

- POS (type I) frequency per 28 days during the Evaluation Period
- Percent reduction in POS (type I) frequency per 28 days from Baseline of the previous study to the Evaluation Period
- Responder rate for POS (type I) frequency over the Evaluation Period. A responder is defined as a subject with a  $\geq 50\%$  reduction in seizure frequency from the Baseline Period of the previous study

Other efficacy variables:

For subjects with focal-onset epilepsy:

- Percentage of subjects continuously seizure-free for all seizure types (I+II+III) for at least 6 months and at least 12 months during the Evaluation Period

For subjects with generalized epilepsy:

- Generalized (type II) seizure days per 28 days during the Evaluation Period
- Percent reduction in generalized (type II) seizure days per 28 days from Baseline of the previous study to the Evaluation Period
- Responder rate for generalized (type II) seizure days over the Evaluation Period. A responder is defined as a subject with a  $\geq 50\%$  reduction in seizure days from the Baseline Period of the previous study

- Percentage of subjects continuously seizure-free for all seizure types (I+II+III) for at least 6 months and at least 12 months during the Evaluation Period

The following will be evaluated separately for subjects with focal-onset epilepsy and subjects with generalized epilepsy:

- Change in Patient Weighted Quality of Life in Epilepsy Questionnaire (QOLIE-31-P) scores from Baseline of the previous study to each assessment for the first 2 years and to the last Evaluation Period assessment during the first 2 years
- EuroQol 5 Dimensions (EQ-5D) questionnaire response for each assessment for the first 2 years for the Evaluation Period and for the last assessment during the first 2 years of the Evaluation Period

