2.2 Study variables

2.2.1 Safety variables

2.2.1.1 Primary safety variables

- Occurrence of a treatment-emergent adverse event (TEAE)
- Withdrawal due to adverse event (AE)
- Occurrence of a serious adverse event (SAE)

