3.2 Analysis time points

3.2.1 First and last dose of BRV

Unless otherwise noted, all references to the first dose of BRV in this SAP refer to the first dose of BRV during N01199 (ie, not the first dose of BRV from the previous study in which subjects participated in prior to N01199). Unless otherwise noted, all references to the last known dose of BRV in this SAP refer to the last dose of BRV taken across any study periods (ie, not necessarily the last dose of BRV during the Evaluation Period).

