3.2.3 Study Entry Visit

The study Entry Visit (EV) corresponds to assessments performed at the time of entry into N01199. There are 3 groups of subjects to consider:

1. Subjects who immediately entered N01199 after completing the Treatment Periods for N01193, N01252, N01253, and N01254.
2. Subjects who entered the Down-Titration Period of the previous study and entered N01199 during the Down-Titration Period.
3. Subjects who did not immediately enter N01199 and had a gap in treatment with study drug between the previous study and N01199.

Subjects in Categories 1 and 2

Subjects in categories 1 and 2 will generally not have any interruption in study drug dosing during the transition to N01199. For such subjects, selected assessments from the following visits from the previous study will be summarized at EV:

| Study | Visit (Time Point) |
|---------------|---------------------------|
| N01193 | Visit 4 (Week 7) |
| N01252/N01253 | Visit 7 (Week 12) |
| N01254 | Visit 8 (Week 16) |

The following assessments were to be performed for all subjects at the above time points: laboratory parameters, vital signs, and ECGs; the results for these assessments will be summarized at EV. Other assessments were to be performed at the above time points but will not be summarized. QOLIE-31-P, HADS, EQ-5D and social-professional data were only assessed at the above time points for studies N01252, N01253, and N01254.

The body weight recorded at the above study visits for the previous studies will be summarized for EV.

Subjects in Category 3

Some subjects in category 3 have data available from an SEV at the time of entry into N01199. Laboratory parameters, vital signs, and ECGs collected at SEV will be summarized at EV. If one or more of these assessments were not performed at SEV, or if a subject in category 3 does not have an SEV, then the subject will be excluded from EV for the assessments that were not performed, regardless of the duration of time the subject was not receiving the study drug after the previous study.

QOLIE-31-P, HADS, EQ-5D, and socio-professional data will not be summarized at EV for subjects in category 3 regardless of the duration of time the subject was not receiving study drug after the previous study.

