11.2.2 General summaries of TEAEs

Pre-treatment AEs will be provided in a subject data listing; no summaries of pre-treatment AEs are planned.

An overall summary of AEs will provide the overall number of TEAEs and the numbers and percentages of subjects with at least 1 TEAE, with a TEAE that led to permanent discontinuation of study drug, with a drug-related TEAE, with a severe TEAE, with a treatment-emergent SAE, and with a drug-related treatment-emergent SAE. The number and percentage of subjects who died will also be summarized. This summary will be provided for all subjects in the Safety Analysis Set and also by subgroup for geographic region and seizure type.

The following summaries of TEAEs will be provided by MedDRA SOC and PT. All summaries are for the combined Evaluation, Down-Titration, and Post-Treatment Periods unless otherwise indicated.

Overall Incidence Summaries

- Incidence of TEAEs
- Incidence of TEAEs by 3-month time interval
- Incidence of TEAEs by study period (Evaluation, Down-Titration, Post-Treatment)
- Incidence of TEAEs for TEAEs occurring in at least 5% of subjects
- Incidence of TEAEs by 3-month time intervals for TEAEs occurring in at least 5% of subjects overall
- Incidence of non-serious TEAEs occurring in at least 5% of subjects

The incidence of TEAEs occurring in at least 5% of subjects will be summarized overall as noted above and also by subgroup for geographic region, seizure type, and randomized treatment from the previous double-blind study.

A subject is included in a 3-month interval if the subject was receiving BRV at any time during that interval based on their duration of exposure to BRV (eg, a subject with exposure for 91 days is included in the time interval for Months 1-3 and Months 4-6). Summaries of AEs by 3-month intervals will include all subjects who are classified into each time interval

as defined above. TEAEs which had onset prior to or on the date of the last dose of BRV are included in summaries by 3-month time intervals.

Maximum Intensity and Causality

- Incidence of TEAEs by maximum intensity
- Incidence of drug-related TEAEs

Serious Adverse Events

- Incidence of treatment-emergent SAEs

Discontinuations due to TEAE

- Incidence of TEAEs leading to permanent discontinuation of study drug

TEAEs of interest

AEs of interest will be identified based on MedDRA search criteria, which are documented outside of the SAP. The following summaries will be provided for AEs of interest:

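### The AE tables for the primary variable of withdrawal due to an AE count only events starting on or after the first N01199 dose, so withdrawals for unchanged carried-over AEs appear only in disposition and a listing

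*SAP*

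**What the plan says.** Protocol 13.1.2 lists three primary safety variables. The first is restricted to treatment-emergent events. The second is "Withdrawal due to an AE", with no such restriction, and SAP 2.2.1.1 repeats it in equivalent words. Protocol 13.1.3 then plans separate tables for AEs that led to withdrawal.

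The SAP sets the clock in 3.2.1: the first dose of BRV is the first one in N01199, "not the first dose of BRV from the previous study in which subjects participated in prior to N01199". SAP 11.2.1 builds on this: "Pre-study AEs are defined as AEs which had onset prior to the date of the first dose of BRV". A TEAE is an AE starting on or after the day of that dose.

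SAP 11.2.2 reports discontinuation twice, once as a line in the overall AE summary and once as a SOC/PT table, "Incidence of TEAEs leading to permanent discontinuation of study drug". Both cover TEAEs only. Earlier-onset events go to a subject listing, and "no summaries of pre-treatment AEs are planned".

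Protocol 11.1.15 says that at the Entry Visit "the Investigator will record any adverse event that was still ongoing at the end of the previous study". SAP 3.2.3 says of most routes into the study: "Subjects in categories 1 and 2 will generally not have any interruption in study drug dosing during the transition to N01199".

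**The concern.** For a subject from a BRV arm who rolls over without a gap, the first N01199 dose does not mark the start of treatment. An AE that began on BRV in the previous study and persists is nevertheless classed as pre-study. If the subject later stops BRV in N01199 because of it, that is a withdrawal due to an AE as both documents word the variable, but it does not enter the tables that show which events drive withdrawal.

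Entrants had completed the previous study (SAP 2.3), so a later withdrawal for a carried-over AE is an N01199 event. If the N01199 AE tables omit it, no event-level summary in this plan shows it. At stake are the AE-table rate for a primary safety variable and its breakdown by event, most plausibly in the first months after roll-over.

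**Working it through.** The plan states no AE-withdrawal rate and no count of carried-over AEs, so there is no figure to reproduce. The check is mainly textual.

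**Step 1: scope of the variable against scope of the tables.**

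| Place | Events covered | Onset condition |
|---|---|---|
| Protocol 13.1.2, SAP 2.2.1.1 (variable) | AEs causing withdrawal | None |
| Protocol 13.1.3 (planned table) | AEs causing withdrawal | None stated |
| SAP 11.2.2, overall summary | TEAEs causing permanent stop of BRV | On or after day of first N01199 dose |
| SAP 11.2.2, SOC/PT table | TEAEs causing permanent stop of BRV | Same |
| SAP 5.1, disposition | Primary reason for discontinuation is an AE | None, but no event term |
| SAP 11.2.2, listing | Earlier-onset AEs | Before first N01199 dose |

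SAP 11.2.2 gives no reason for using the narrower set.

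**Step 2: which carried-over AEs drop out of the AE tables.**

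- Protocol 12.1.1 requires reporting of AEs that recur or worsen after the initial visit. Protocol 12.1.5 has an unexpected rise in intensity reported again with its own start date. Such a record can qualify as a TEAE and be counted.
- SAP 11.2.1 treats an incomplete onset date that matches the month or year of the first dose as treatment-emergent. Some carried-over AEs are counted that way.
- What remains is an AE with a known earlier onset that stays unchanged, or progresses as expected, and for which the subject later stops BRV. It has no new record, so it is not a TEAE.

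**Step 3: size per subject.** The input is 668 enrolled (SAP 2.4). The Safety Analysis Set may be smaller.

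Understatement in percentage points = 100 × k / 668, where k is the number of omitted subjects.

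- k = 1: 100 × 1/668 = 0.15
- k = 5: 100 × 5/668 = 0.75
- k = 10: 100 × 10/668 = 1.50
- k = 20: 100 × 20/668 = 2.99

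**Step 4: a range under assumed rates.** Let c be the share entering with an ongoing AE and w the share of those who withdraw for it without a new AE record. Neither is in the documents. Then k = 668 × c × w.

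- c = 10%, w = 1%: 668 × 0.10 × 0.01 = 0.7 subjects (0.1 points)
- c = 30%, w = 2%: 668 × 0.30 × 0.02 = 4.0 subjects (0.6 points)
- c = 50%, w = 5%: 668 × 0.50 × 0.05 = 16.7 subjects (2.5 points)

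**Step 5: direction.** Removing the onset condition can add subjects to the table but cannot remove any. Compared with the variable as worded, the restriction can therefore only lower the rate.

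**The case against.** The best defence is that the variable is reported elsewhere. SAP 5.1 counts discontinuations by primary reason for the Safety Analysis Set, overall and by region and seizure type, with adverse event as its own category and no onset condition. A reader might infer from SAP 11.2.2 alone that these withdrawals are not analysed at all. The documents do not support that: the subjects are counted in disposition, and the causing event should be traceable because earlier-onset AEs are listed and the CRF records action taken with study drug. This part of the defence stands. It does not supply the SOC/PT breakdown or correct the AE-table rate.

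A reader might also infer that every carried-over AE that becomes intolerable is missed. That goes too far. Intensity is graded partly by interference with usual activities (protocol 12.1.3), so such an AE may well move up a grade, be reported again and count as a TEAE. Nor did every carried-over AE begin on BRV, since SAP 2.3 describes the previous studies as placebo-controlled.

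It is tempting, too, to say that the AE table must show fewer withdrawals than disposition. It need not. Disposition generally takes one primary reason, while the AE table takes any TEAE for which drug was stopped. A subject with a contributory TEAE but another primary reason is in the AE table only. The two counts can differ in either direction for reasons unrelated to onset.

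Finally, the AEs in protocol 13.1.3 could be read as shorthand for TEAEs, because the preceding sentence concerns TEAEs. The variable list in 13.1.2 weakens that reading: it uses the narrower term for one primary variable and the broader term for the next.

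**Conclusion.** The point holds for the AE tables. SAP 11.2.2 reports a primary safety variable on a narrower set of events than the variable's own wording, and the cut-off falls within continuous study treatment for most routes of entry. Withdrawals for carried-over AEs without a new record are missing from the AE-table rate and from the event breakdown. They are not missing from the report as a whole.

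The size is unknown. It is 0.15 percentage points per omitted subject, taking the 668 enrolled as denominator. The assumed shares above give roughly 0.1 to 2.5 points, but that range illustrates the arithmetic and is not an estimate. The study is descriptive and tests no hypothesis, so no inference is affected. The case for a change is that the restriction works in one direction on a primary safety variable and is cheap to remove.

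**What to change.** In SAP 11.2.2, add a SOC/PT table of all AEs for which BRV was permanently stopped in N01199, whatever their onset date. Split it by onset before versus on or after the first N01199 dose. Within the earlier group, split by previous randomised treatment (placebo or BRV), which SAP 4.8 already uses for TEAE subgroups. Footnote any difference from the SAP 5.1 count. Exact agreement should not be promised, because the two tables count different things.

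A table of all AEs ongoing at entry is not needed, since it does not measure withdrawal. The split by previous randomised treatment will not separate AEs that began on BRV from those that began before any BRV. That would need previous-study dosing dates, and the sections cited here do not show whether the N01199 data hold them.

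The cost is a wording change and one extra table, using AE records and action-taken codes already in the CRF. The reported AE-withdrawal rate may be slightly higher.

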#### **10.1.2 Dosing Schedule**

Subjects coming from BRV studies have the opportunity to access BRV treatment at a flexible dose of up to a maximum of 200 mg/day in b.i.d. administration. It is recommended that the daily dose be divided equally, taken with or without food, and that the first intake will be in the evening of the day of the dispensation of the study medication.

The individual starting dose of each subject will be the one defined/reached at the end of the previous study. It is recommended that the dosing be done in even increments such as 20 mg, 30 mg, 40 mg, etc. with the implementation of the IVRS/IWRS.

At each subject visit, if necessary, the dosage can be adapted:

- Up-titration can be made by increments of maximum 50 mg/day on a weekly basis and this to a maximum of 200 mg/day.
- Dose decreases can be made by steps of maximum 50 mg/day on a weekly basis. A last down-titration step at 20mg/day for 1 week will be included prior to the study-drug free period.

At each visit, an IVRS/IWRS will be responsible for issuing subjects kits of study medication, as appropriate, according to the visit schedule and according to the supplies needed by the subject in terms of number of containers of each size (80 or 200) and of each dosage (10 mg or 25 mg tablets) according to the dose prescribed and the possibility to down-

titrate/up-titrate by a maximum of 50 mg/day steps. Containers of 80 tablets will be progressively removed.

In case the subject will not continue with BRV, the Investigator will plan the progressive down-titration of the study drug. The down-titration period will be followed by a period free of study drug of minimum 2 weeks and a maximum of 4 weeks and subsequently the Final Visit will occur.

At the time of study termination by the Sponsor (as defined in Section 8.4), subjects will discontinue the study drug following the described down-titration process or will be converted without down-titration to commercial BRV, when and where available. Alternatively, subjects may transition into another BRV study, or be initiated without down-titration in a managed access program, named patient program, compassionate use program, or similar type of access program as allowed per country-specific legal and regulatory requirements.

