## **11.2 Description Visit by Visit**

The Entry Visit will be performed on the same day as the last visit of the previous study in which the subject was enrolled. Should an interval become necessary between the last visit of the previous study and the entry visit in the present study, the Sponsor's Study Physician or representative should be contacted for agreement. The Adverse Events, Medical Procedures, Non-Antiepileptic and Antiepileptic Concomitant Medication belonging to the interim period will be reported in the CRF, on specific pages.

Each visit will be planned within a "window" of  $\pm 7$  days from the previous visit.

At any time, the subject may have an additional study visit/phone call if the Investigator of the subject deems it necessary. All information, including the reason for the visit/phone call, any information on adverse events, etc., should be collected in the source documents and recorded in the appropriate section of the CRF.

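### The partial-date rule in SAP 11.2.1 can count an AE as treatment-emergent even when other recorded data show that it began before the first N01199 dose

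*SAP*

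**What the plan says.** SAP 11.2.1 sorts AEs into two classes by onset date. "Pre-study AEs are defined as AEs which had onset prior to the date of the first dose of BRV", and an onset on or after the calendar day of first dose makes the event a TEAE. SAP 3.2.1 fixes the reference point: unless otherwise noted, such references "refer to the first dose of BRV during N01199", not in the earlier study.

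A separate sentence handles missing date parts: "AEs with an incomplete onset date will be classified as TEAEs if the month and year of onset" match those of the first dose, or, failing a known month, if "the year of onset (when only year is specified) is the same as the year of first BRV dose". No other condition is attached.

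The protocol brings events from before N01199 dosing into the database by design:

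- **Protocol 11.1.15:** "At the Entry Visit, the Investigator will record any adverse event that was still ongoing at the end of the previous study".
- **Protocol 11.2:** where there is an interval between studies, the AEs "belonging to the interim period will be reported in the CRF, on specific pages".
- **Protocol 12.1.3:** a date of outcome is recorded for each AE that has ended.

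On dose timing, Protocol 10.1.2 recommends that "the first intake will be in the evening of the day of the dispensation of the study medication". Protocol 11.2 normally puts the Entry Visit on the same day as the last visit of the previous study.

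**The concern.** The rule looks only at the partial onset date. In a rollover study some partially dated AEs will have another record that settles the order of events, such as an end date before the first dose, an interim-period entry, or a previous-study record. The rule ignores that evidence and assigns the event to N01199 treatment.

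The flag has wide use. Occurrence of a TEAE is a primary safety variable (SAP 2.2.1.1). SAP 11.2.2 builds the drug-related, severe, serious and discontinuation counts on it. Pre-treatment AEs are only listed, so the flag decides whether an event is tabulated at all. The TEAEs reported in at least 5% of subjects are also tabulated by randomized treatment in the previous study, so an event that began on placebo could appear as emergent on BRV.

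**Working it through.** The plan gives no figure on this point. The check therefore applies the rule literally and then asks how often a pre-dose onset would meet it.

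**1. The rule applied to an illustrative first dose on 20 June 2009**

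| Recorded onset | Other evidence | As written | With the fix |
|---|---|---|---|
| 5 June 2009 | none needed | pre-study | pre-study |
| June 2009 | end date before 20 June | TEAE | pre-study |
| 2009 only | previous-study record shows onset before 20 June | TEAE | pre-study |
| June 2009 | none | TEAE | TEAE |
| April 2009, June 2008 or 2008 only | none | matching rule not triggered | unchanged |

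Only rows two and three change. The same event is pre-study with a full date and treatment-emergent with a partial one.

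**2. No other text corrects this.** The date imputation in SAP 6.4 concerns medications. SAP 11.2.2 uses the TEAE flag as 11.2.1 delivers it.

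**3. Chance that a pre-dose onset matches.** Assumptions: the first dose is uniform over a 365-day year, and onset is uniform over the T days before it. T is 7, 12 or 16 weeks, the time points of the previous-study visits in SAP 3.2.3, so T = 49, 84 or 112 days.

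- *Year only.* An onset t days before dosing falls in the previous year with probability t/365. Averaged over t = 1 to T, the match probability is 1 − (T + 1)/(2 × 365).
- *Month and year.* A dose date has on average Σ L(L − 1)/2 ÷ 365 earlier days in its own month, where L is the month length. That is (7 × 465 + 4 × 435 + 378)/365 = 5373/365 = 14.7 days. The match probability is 14.7/T.

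| Previous study | T (days) | Year-only match | Month-and-year match |
|---|---|---|---|
| N01193 | 49 | 1 − 50/730 = 93% | 14.7/49 = 30% |
| N01252, N01253 | 84 | 1 − 85/730 = 88% | 14.7/84 = 18% |
| N01254 | 112 | 1 − 113/730 = 85% | 14.7/112 = 13% |

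A day-by-day enumeration gives the same percentages. Among partially dated AEs with onset in that window, most year-only dates and a minority of month-and-year dates would match.

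**4. Weight per subject.** SAP 2.4 gives 668 enrolled. If all are in the Safety Analysis Set, one subject is 100/668 = 0.15 percentage points, five are 0.75 and ten are 1.5. A subject who has another TEAE anyway adds nothing to the overall incidence. The 5% reporting threshold is 0.05 × 668 = 33.4, that is, 34 subjects. Subgroup denominators are smaller, and the documents do not give them.

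**The case against.** The best defence is that this is a deliberate worst-case convention. SAP 11.2.2 also resolves gaps against the drug: missing intensity counts as severe and missing causality as related. In a single-arm, descriptive study, modest over-counting of TEAEs is tolerable. The partial-date sentence is also a specific rule that overrides the general definition, so a programmer faces no ambiguity. Both arguments stand for dates that cannot be resolved. They do not justify setting aside a record that does resolve the date, because the missing day is then no longer an open question.

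Four stronger readings are tempting but not supported.

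- *Carried-over AEs in general become TEAEs.* They do not. Fully dated ones are correctly pre-study, and when the month is known both month and year must match.
- *Every AE noted as ongoing at the Entry Visit is pre-study.* The definition works by calendar day. An AE that starts on the morning of a same-day rollover is ongoing at entry, yet has its onset on the day of first dose and is a TEAE.
- *The number affected can be estimated.* If 30% of subjects carried an AE over and 2–5% of those AEs were partially dated, 668 × 0.30 × 0.02 to 0.05 gives 4 to 10 subjects. Multiplying by 0.13 to 0.93 gives about 0.5 to 9. Both rates are pure assumptions, and the completed-field and data-cleaning requirements in Protocol 15.4 and 15.7 should keep partial dates uncommon.
- *Preferred-term or discontinuation tables would be visibly distorted.* Nothing in the documents allows that to be calculated.

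It is also fair to say that the CRF is not available here. End dates and interim-period pages are described, but a field marking an AE as carried over is not.

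**Conclusion.** The point holds as a minor correction to the definition of a primary safety variable. The partial-date rule can override recorded evidence of earlier onset and so produce a result that the section's own definition of a pre-study AE excludes. An AE that stopped before the first dose should arise mainly in subjects with a treatment gap (category 3 in SAP 3.2.3); a carried-over AE can arise in any subject.

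The effect is probably small and runs towards overstating TEAEs, so it does not flatter the drug. The match percentages depend on the uniform-onset and uniform-dose assumptions, and they are conditional on an AE being partially dated. They do not give a count. The ceiling of 0.15 percentage points per subject assumes a Safety Analysis Set of 668.

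**What to change.** Add to SAP 11.2.1 that an AE with an incomplete onset date is classed as pre-study if other recorded data show onset before the date of the first N01199 dose. Qualifying evidence would be any of:

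- an end date before that date;
- an interim-period CRF entry dated before it;
- an Entry Visit or previous-study record showing onset before it. Being ongoing at entry is not enough by itself when the previous study's last visit and the first dose fall on the same day.

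State also what does not change. The month/year matching rule stays for every unresolved partial date. AEs that start on the day of first dose stay TEAEs. A worsening reported as a repeated AE under Protocol 12.1.5, with its own start date on or after first dose, stays a TEAE.

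The cost is one sentence and one extra derivation check, with no change to study conduct. The previous-study branch needs a look-up in the earlier databases, and the team should confirm which CRF fields support it. The downside is a slightly less conservative flag for these few records.
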